## 8 Research Question and Objectives

The aim of this study is to expand knowledge on the effectiveness of Avelumab 800 mg intravenous infusion flat-dose treatment in combination with Axitinib 5 mg orally twice per day as the first-line therapy in patients with advanced RCC in addition to safety and tolerability under routine conditions of daily clinical practice.

### 8.1 Primary Objective

- To determine OS rate at 12 months after the index date (baseline visit)

### 8.2 Secondary Objectives

- To determine OS rate at 24 months after the index date
- To assess duration of OS
- To evaluate ORR and disease control rate (DCR) up to 24 months after the index date
- To assess duration of response (DoR)

- To assess duration of PFS on Avelumab plus Axitinib therapy and progression-free survival 2 (PFS2) on Avelumab plus Axitinib therapy followed by the second-line treatment
- To assess the health-related quality of life (HRQoL) using the National Comprehensive Cancer Network/Functional Assessment of Cancer Therapy-Kidney Symptom Index 19 (NCCN-FACT FKSI-19) at the index date and at every third cycle of Avelumab treatment (intervals of about 6 weeks) thereafter, until the end of treatment or end of 24 months of study follow-up period, whichever occurs first
- To analyze the nature, severity, duration, frequency, and timing of AEs that occurred from the index date up to 90 days post discontinuation of Avelumab plus Axitinib or completion of the 24 months (i.e., end of the study) follow-up from the index date, whichever occurs first
- To assess time to therapy discontinuation due to AE  $\geq$  Grade 3
- To assess therapy modifications due to AE related to Avelumab plus Axitinib therapy and management of AE related to Avelumab plus Axitinib therapy
- To determine percentage of patients receiving later-line therapy and frequency distribution of later-line therapy regimens among patients progressing on Avelumab plus Axitinib
- To assess time to second-line therapy initiation
- To assess patient-reported potential signs and symptoms of immune-related AEs

## 9 Research Methods

## 9.1 Study Design

### 9.1.1 Design Overview

[figure not shown]
This study is a prospective, international, single-arm, observational real-world study in patients with advanced RCC. This multicenter study will be conducted at approximately 30 centers in various European countries. A total of approximately 100 patients, who are currently receiving Avelumab (800 mg intravenously every 2 weeks) plus Axitinib (5 mg orally twice per day) in accordance with the terms of the marketing authorization for the first-line therapy, will be selected. Patient assignment to Avelumab plus Axitinib therapy should be decided in advance by the treating physician and fall within current clinical practice prior to study enrollment. There will not be any study-specific interventions in this study. The study size is further described in [Section 9.5](#).

The index date (baseline visit) is defined as the first administration date, after informed consent, of Avelumab plus Axitinib therapy to patients with advanced RCC. Patients will be recruited over a period of approximately 24 months and will be followed up for 24 months from the index date, irrespective of whether they continue or discontinue the study treatment. There will be a safety follow-up at 90 days post discontinuation of Avelumab plus Axitinib therapy.

Study visits will be scheduled according to routine clinical practice in terms of visit frequency and types of performed treatments and assessments. Due to the observational nature of this study, planned assessments will be recorded as part of routine clinical practice, in line with the approved SmPC and as clinically indicated.

Figure 1 below provides a schematic overview of the study design.

### Figure 1 . Overview of the Study Design

W=Week, HRQoL=Health-related quality of life, NCCN-FACT FKSI-19=National Comprehensive Cancer Network/Functional Assessment of Cancer Therapy-Kidney Symptom Index 19

### 9.1.2 Outcomes

#### 9.1.2.1 Primary

The primary effectiveness outcome is:

- OS rate at 12 months after the index date
  - Percentage of patients who are still alive at 12 months after the index date

#### 9.1.2.2 Secondary

Secondary effectiveness outcomes:

- OS rate at 24 months after the index date
  - Percentage of patients who are still alive at 24 months after the index date
- OS
  - Time interval from the index date to the date of death from any cause
- ORR up to 24 months after the index date
  - Percentage of patients with complete response (CR) or partial response (PR), as best overall response up to 24 months after the index date according to the investigator assessment

- DCR up to 24 months after the index date
  - Percentage of patients with CR, PR, or stable disease (SD), as best overall response up to 24 months after the index date according to the investigator assessment
- DoR
  - DoR is defined as the time from the first CR or PR criteria met, whichever was reported earlier, until the date of documented overall disease progression

**Note:** CR, PR, SD, progressive disease (PD) will be defined as per Response Evaluation Criteria in Solid Tumours (RECIST) version 1.1 ([Eisenhauer 2009](#))

### **Progression-free survival:**

- PFS
  - Time interval from the index date to the date of disease progression or death from any cause, whichever comes first
- PFS2
  - Time interval from the index date to the date of disease progression on second-line treatment or death from any cause, whichever comes first

### **Patient-reported outcomes:**

- HRQoL using the NCCN-FACT FKSI-19 at the index date and at every third cycle of Avelumab treatment (intervals of about 6 weeks) thereafter until the end of treatment or end of 24 months of study follow-up, whichever occurs first
  - The NCCN-FACT FKSI-19 is a 19-item self-reported questionnaire that captures symptom severity and interference in activity and general health perceptions ([Rothrock 2013](#), [Rao 2009](#))
  - The NCCN-FACT FKSI-19 covers 4 subscales of the FKSI:
    1. DRS-P, disease-related symptoms subscale—physical
    2. DRS-E, disease-related symptoms subscale—emotional
    3. TSE, treatment side effects subscale
    4. Functional and well-being (FWB), function and well-being subscale ([Rao 2009](#))
  - Each of the items is scored on a five-point scale from zero (not at all) to 4 (very much).

### **Safety and tolerability:**

- Frequency and nature of all-cause AEs according to Medical Dictionary for Regulatory Activities (MedDRA) system organ class (SOC) and preferred term (PT) that occurred from the index date up to 90 days post discontinuation of Avelumab plus Axitinib or completion of the 24 months (i.e., end of the study) follow-up from the index date, whichever occurs first
- Frequency of all-cause AEs by maximum Common Terminology Criteria for Adverse Events (CTCAE) grade that occurred from the index date up to 90 days post discontinuation of

Avelumab plus Axitinib or completion of the 24 months (i.e., end of the study) follow-up from the index date, whichever occurs first

- Frequency of all-cause AE  $\geq$  Grade 3 leading to discontinuation of Avelumab plus Axitinib summarized by MedDRA SOC and PT
- Duration of Avelumab plus Axitinib therapy among patients who discontinued the study drug due to all-cause AEs  $\geq$  Grade 3
- Time to onset of all-cause AEs defined as the time interval from the index date to the onset of AE
- Duration of all-cause AEs defined as the time interval between the onset and resolution of AE
- Outcome of all-cause AEs: resolved, resolving, not resolved, resolved with sequelae, fatal, unknown
- Percentage of patients with therapy modifications due to AE related to Avelumab plus Axitinib therapy (e.g., therapy interruptions and reductions of infusion rate for Avelumab, therapy interruptions, and dose reductions for Axitinib)
- Frequency and type of medical intervention or medications used for the management of AE related to Avelumab plus Axitinib therapy (e.g., use of corticosteroids, antihypertensive therapy, treatment for thyroid dysfunction, measures to decrease hemoglobin, and hematocrit)
- Percentage of patients receiving later-line therapy and frequency distribution of later-line therapy regimes among patients progressing on Avelumab plus Axitinib including the names of medications of monotherapy/combination treatment used in second-line and third-line therapy
- Time to second-line therapy initiation is defined as the time from Avelumab plus Axitinib therapy discontinuation to the initiation of second-line therapy
- Frequency of patient-reported potential signs and symptoms of immune-related AEs (the investigator or the treating physician will explain signs and symptoms of potential immune-related AEs to patients; immune-related AEs may include immune-mediated pneumonitis, immune-mediated colitis, immune-mediated hepatitis, immune-mediated endocrinopathies, immune-mediated nephritis with renal dysfunction etc.) ([BAVENCIO, SmPC](#))

## 9.2 Setting

### 9.2.1 Study Population

The study population will be identified according to the below inclusion and exclusion criteria. For inclusion in the study, all of the following inclusion criteria must be fulfilled:

1. Adult patient, age  $\geq$  18 years
2. Patient with the Eastern Cooperative Oncology Group (ECOG) performance status 0, 1, or 2 ([Oken 1982](#))
3. Patient with a histologically confirmed diagnosis of RCC with any histological origin

---

4. Patient with a locally advanced/metastatic disease (i.e., newly diagnosed Stage IV RCC per American Joint Committee on Cancer) or has recurrent disease
5. Patient has received 1 or 2 cycles of Avelumab plus Axitinib treatment as a first-line therapy according to the approved SmPC
6. Patient willing to sign the written informed consent form (ICF) to participate in this study

Patients are not eligible for this study if they fulfill any of the following exclusion criteria:

1. Patient with contraindications for Avelumab or Axitinib according to the approved SmPC
2. Patient who has participated in any interventional clinical trial of a drug or device within 28 days prior to the start of Avelumab plus Axitinib

### **9.2.2                   Definition of Study Cohorts and Description of Treatments**

This is a single cohort study enrolling patients with advanced RCC, who are currently receiving Avelumab plus Axitinib in accordance with the terms of the marketing authorization for the first-line therapy. Patient assignment to Avelumab plus Axitinib therapy should have been decided in advance by the treating physician and fall within current clinical practice and prior to study enrollment.

According to the approved SmPC, the recommended dose of Avelumab is 800 mg administered intravenously over 60 minutes every 2 weeks in combination with Axitinib 5 mg orally taken twice per day (12 hours apart) with or without food until disease progression or unacceptable toxicity.

### **9.2.3                   Observation Period**

Each patient will be followed up from the date the ICF is signed until lost to follow-up, withdrawal of consent, death, or the end of the data collection period, whichever comes first. Patients will be followed up for 24 months from the index date, irrespective of whether they continue or discontinue the study treatment.

### **9.2.4                   Frequency of Assessments**

The [Table 1](#) provides the Schedule of Assessments for this study. Patients who sign the ICF and meet all eligibility criteria during the screening will be enrolled in this study. The baseline visit will be at the index date, which is defined as the first administration date, after informed consent, of Avelumab plus Axitinib therapy to patients with advanced RCC. Baseline data will be collected at the index date. The screening visit and the baseline visit may or may not be on the same day.

Patients will attend the sites (hospitals) as per routine clinical practice at the discretion of the treating physician. Therefore, the timing of the visits may vary. Results from physical examinations, vital signs, and body weight will be collected upon availability. Data on treatment response will also be collected upon availability. Patients will be asked to provide HRQoL data using the NCCN-FACT Fksi-19 questionnaires available as electronic patient-reported outcomes (ePRO) questionnaires at the index date and at every third cycle of Avelumab treatment (intervals of about 6 weeks) thereafter, until the end of treatment or end of 24 months of study follow-up period, whichever occurs first. Patients can fill out HRQoL data (ePRO questionnaires) either at their homes or at sites (hospitals) during their scheduled visits as per their convenience. In

exceptional cases, the questionnaires on patient-reported HRQoL data can be completed on paper and transferred into electronic case report form (eCRF) afterwards.

**Table 1. Schedule of Assessments**

Assessment	Screening visit	W0 (Index date/ Baseline visit)	Follow-up visits (between W0 to W104) as per routine clinical practice	W104 (end of study)
Informed consent	X			
Inclusion/exclusion criteria	X	X		
Demographics (year of birth, gender)		X		
Physical examination/ vital signs a		X		
Body weight a		X	X	X
Concomitant diseases b		X		
Concomitant medications c		X	X	X
Cancer history d		X		
ECOG performance status		X		
MSKCC risk group e		X		
IMDC risk group f		X		
HRQoL using the NCCN-FACT Fksi-19 questionnaire g		X	X	X
Safety assessment	X	X	X	X
Avelumab plus Axitinib therapy h		X	X	X
Second-line treatment (if Avelumab plus Axitinib discontinued)			X	X
Third-line treatment (if second-line treatment discontinued)			X	X
Treatment response i			X	X
Treatment for AE related to Avelumab plus Axitinib therapy j		X	X	X

AE=Adverse event, ECOG=Eastern Cooperative Oncology Group, HRQoL=health-related quality of life, IMDC=International Metastatic RCC Database Consortium, MSKCC=Memorial Sloan-Kettering Cancer Center, NCCN-FACT Fksi-19=National Comprehensive Cancer Network/Functional Assessment of Cancer Therapy-Kidney Symptom Index 19, W=Week

a Results from physical examinations, vital signs, and body weight will be collected upon availability. Physical examination includes an examination of major body systems. Vital signs include blood pressure (systolic and diastolic) and pulse rate.

b Information on concomitant diseases such as autoimmune disease, cardiovascular disease, hypertension, renal failure, and liver disease.

c Information on concomitant medications such as the use of corticosteroids, anticoagulants, and antibiotics.

d Information on cancer history: age at diagnosis, tumor, node, metastasis (TNM) stage, location of metastases, received nephrectomy, other prior cancer therapies and procedures, expression of the programmed death ligand 1 (PD-L1).

e The MSKCC risk score is based on 5 independent risk factors: low Karnofsky performance status (KPS), low hemoglobin level, high serum lactate dehydrogenase, high corrected serum calcium level, and time from diagnosis to the initiation of systemic therapy of less than 1 year (Heng 2013). The MSKCC risk score categorizes patients into 3 risk groups: 0 (low risk), 1 or 2 (intermediate risk), and  $\geq 3$  (high risk).

f The IMDC risk score is based on data of patients with metastatic RCC treated with targeted therapies and includes 6 risk factors: low KPS, low hemoglobin level, high neutrophil count, high platelet count, high corrected serum calcium level, and time from diagnosis to the initiation of systemic therapy of less than 1 year (Heng 2013). The IMDC risk score categorizes patients into 3 risk groups: 0 (low risk), 1 or 2 (intermediate risk), and  $\geq 3$  (high risk).

g All patients will be asked to fill HRQoL data available as ePRO questionnaires at the index date and at every third cycle of Avelumab treatment (intervals of about 6 weeks) thereafter, until the end of treatment or end of 24 months of study follow-up period, whichever occurs first.

h Avelumab plus Axitinib therapy: data on dose at regular follow-up visits, therapy modifications (change in dose) due to AE, temporary interruption, and treatment discontinuation will be collected upon availability.

i Treatment response includes data on complete response, partial response, stable disease, or progressive disease defined as per RECIST version 1.1. Data on treatment response will be collected upon availability.

j Information on treatment used for the management of AE related to Avelumab plus Axitinib therapy such as use of corticosteroids, antihypertensive therapy, treatment for thyroid dysfunction, measures to decrease hemoglobin, and hematocrit.

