## 9.2.5 Withdrawal from the Study

Patients are free to withdraw from the study at any time without giving their reasons. Patients who discontinue treatment will continue to be followed up until end of the study, as per Schedule of Assessments ([Table 1](#)), regardless of treatment status.

A patient is considered lost to follow-up after 2 documented failed attempts to reach out to the patient. If a patient is lost to follow-up, adequate effort must be made by study center personnel to contact the patient and determine the reason for discontinuation. The measures taken to follow-up on the patient must be documented. If a patient withdraws before completion of study procedures (as described in the Schedule of Assessments in [Table 1](#)), the reason for withdrawal shall be documented in source documents and in the eCRF.

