## **9.5                    Study Size**

In total, approximately 100 patients will be selected from approximately 30 sites in different European countries.

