Continuous variables will be summarized using descriptive statistics, i.e. the number of participants with non-missing values (n), the number of participants with missing values (nmiss), mean, standard deviation (STD), median, 25th percentile (Q1) and 75th percentile (Q3), minimum, and maximum. If there are no missing values, nmiss should be indicated by a 0. Mean, median, Q1, Q3, minimum and maximum will be reported with the same number of decimal places as collected in raw data while STD will be reported with one extra decimal place.

Qualitative variables will be summarized by frequency counts and percentages. Unless otherwise stated the calculation of proportions will be based on the number of participants of the analysis set. Therefore, counts of missing observations will be included in the denominator and presented as a separate category.

If confidence intervals (CIs) are to be calculated, these will be two-sided with a confidence probability of 95%, unless otherwise specified in this IAP.

Time to event data will be summarized descriptively as continuous data and using Kaplan-Meier (KM) analysis. Data summarization will include, when appropriate:

- Plot of KM curve with number at risk
- KM estimates with CI at fixed timepoints (eg, every 6 months) (with number at risk/ failed)
- Median times with CI, and Q1 and Q3.

To provide overall estimates of treatment effects, data will be pooled across sites. The “site” factor will not be considered in statistical models or for subgroup analyses due to the high number of participating sites in contrast to the anticipated small number of participants treated at each site.

All analyses will be performed using Statistical Analysis System (SAS)[®] Software version 9.4 or higher.

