14.1 Primary Endpoint: Overall Survival Rate at 12 Months

14.1.1 Primary Objective: Derivation and Analysis of the Primary Endpoint: Overall Survival Rate at 12 Months

Endpoint Derivation

OS Rate at 12 months	OS rate is defined as the percentage of patients who are alive at 12 months after the index date. OS rate will be presented along with 95% CI. Percentage of patients alive at the time of outcome assessment (12 months) will be calculated as per the KM approach.
-----------------------------	--

[REDACTED]
[REDACTED]
[REDACTED]
[REDACTED]
[REDACTED]
(collected in “[REDACTED]” eCRF page)

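### The primary endpoint is survival at 12 months, but no vital-status check is scheduled near month 12, so patients who leave the site after progression may be censored informatively

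*Protocol*

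**What the plan says.** Protocol section 9.1.2.1 defines the primary outcome as "Percentage of patients who are still alive at 12 months after the index date". SAP section 14.1 adds: "Percentage of patients alive at the time of outcome assessment (12 months) will be calculated as per the KM approach". Protocol section 9.5 sets the size: "approximately 100 patients will be selected from approximately 30 sites".

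Table 1 has 18 rows, none of them survival or vital status. Its columns are screening, W0, W104 and, between the last two, "Follow-up visits (between W0 to W104) as per routine clinical practice". Section 9.2.4 explains: "Patients will attend the sites (hospitals) as per routine clinical practice at the discretion of the treating physician".

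On follow-up after treatment, protocol section 9.2.5 says: "Patients who discontinue treatment will continue to be followed up until end of the study, as per Schedule of Assessments". Sections 9.1.1 and 9.2.3 set 24 months of follow-up from the index date regardless of treatment status. Section 9.1.1 also provides a safety follow-up 90 days after discontinuation, and section 11.4 calls that period mandatory.

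On loss, section 9.2.5 says: "A patient is considered lost to follow-up after 2 documented failed attempts to reach out to the patient". It then asks sites to make and document an adequate effort to contact the patient and learn why they discontinued. Under section 9.2.3, being lost ends observation.

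SAP section 14.2 censors OS at last contact when no death is recorded. SAP section 9.6 builds that date from visits, assessments, AE dates, drug dates and termination pages, and admits only dates tied to actual examinations.

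**The concern.** Kaplan-Meier does not need a visit exactly at month 12. It needs vital status to be known through month 12, or censoring before then to be unrelated to prognosis. In this study the most plausible reason to drop out of sight is progression followed by a move to another hospital or to palliative care. Such patients die sooner than those who remain under observation, yet the estimator gives them the hazard of those who remain.

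Scheduled data capture also thins out at that point: HRQoL stops with treatment, and mandatory AE recording can end 90 days after discontinuation. Survival is the primary outcome, yet it has no row of its own, while body weight and concomitant medication do. There is no comparator arm in which such a bias could partly cancel, and a confidence interval does not reveal it.

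**Working it through.** **Does the existing text close the gap?**

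- The 24-month follow-up in section 9.2.5 is to be done according to Table 1, which has no survival row.
- The 90-day safety follow-up is a real contact for patients who stop treatment. For a patient who stops at month 5, however, it falls near month 8, and no vital-status contact is fixed between then and month 12.
- The effort to reach lost patients aims at the reason for discontinuation, and the only route named is the patient.
- The SAP's 12 Months window (section 9.7, days 316 to 410) maps visits that happen to occur. It does not require one.
- SAP section 15.2.1 lists dates and reasons of death, so the eCRF captures deaths. The visible text does not say when a site must look for them.

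**How large could the effect be?** The visible text gives no loss rate, no expected OS rate and no precision figure, so there is no plan figure to reproduce. The inputs are:

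- Median PFS 13.5 months, between the 13.3 and 13.8 quoted for avelumab plus axitinib in protocol section 7. An exponential form is assumed, with every PFS event treated as progression.
- Death hazard after progression, μ = 0.06 or 0.08 per month (assumed).
- Share q of progressors untraced: 10, 20 or 30% (assumed). They are last seen d = 0 or 3 months after progression; d = 3 approximates the 90-day follow-up.

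Formulas, with λ = ln 2 / 13.5 = 0.0513 per month:

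- Alive without progression: A(t) = exp(−λt).
- Alive after progression: B(t) = λ/(μ−λ) × [exp(−λt) − exp(−μt)].
- True OS at 12 months: A(12) + B(12) = 0.540 + 0.316 = 85.6% for μ = 0.06, and 0.540 + 0.282 = 82.2% for μ = 0.08.
- Still observed after progression: B_o(t) = B(t) − q·exp(−μd)·B(t−d), where the second term is zero for t < d.
- Large-sample Kaplan-Meier value: exp(−∫ μB_o/(A+B_o) dt), integrated from 0 to 12.
- Percent censored before month 12: 100·q·[1 − exp(−λ(12−d))]·exp(−μd).

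Results (differences taken before rounding):

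| μ | d (months) | KM at 12 months for q = 10 / 20 / 30% | Overstatement (points) | Censored early (per 100) |
|---|---|---|---|---|
| 0.06 | 0 | 86.6 / 87.7 / 88.8% | +1.0 / +2.1 / +3.2 | 4.6 / 9.2 / 13.8 |
| 0.06 | 3 | 86.1 / 86.6 / 87.2% | +0.5 / +1.0 / +1.6 | 3.1 / 6.2 / 9.3 |
| 0.08 | 0 | 83.4 / 84.7 / 86.2% | +1.3 / +2.6 / +4.0 | 4.6 / 9.2 / 13.8 |
| 0.08 | 3 | 82.8 / 83.4 / 84.1% | +0.6 / +1.2 / +1.9 | 2.9 / 5.8 / 8.7 |

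**Sensitivity to the model.** A second version allows death without progression (0.002 to 0.008 per month, assumed), uses median PFS 13.8 months, and sets true OS between 78.3% and 89.9%. Those are the one-year rates of another trial's arms in protocol section 7, used only as a range. With loss at progression, the overstatement is +0.1 to +1.4 points at q = 10%, +0.2 to +3.6 at 25% and +0.4 to +7.9 at 50%.

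**Yardstick.** The exact 95% interval for 85/100 is 76.5 to 91.4%, a half-width of 7.4 points (8.5 at 78/100, 6.4 at 90/100). These assume complete status at month 12.

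**The case against.** The strongest reply is that the protocol already demands follow-up. A reader might infer from Table 1 that a patient who leaves the site need not be contacted, that two failed attempts close the case, or that W104 is the only fixed point after baseline. The documents support none of these. Follow-up runs 24 months irrespective of treatment, effort to reach a lost patient must be made and documented, and the 90-day safety follow-up applies to the patients most at issue. Fatal outcomes within that period are recorded as SAEs (section 11.4), and the exemption for disease progression does not cover them (section 11.5). This part of the reply stands. It narrows the gap and roughly halves the illustrated bias, but it does not supply a status check at month 12.

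Two further inferences fail:

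- **That withdrawal is all-or-nothing.** This would rest on silence. The protocol does not say so, and the consent pages are not in the public copy.
- **That the interval is too narrow despite lost information.** In a simulation at μ = 0.06 with loss at progression, the mean standard error does fall, from about 3.5 to 3.3 points at q = 30%. That is mainly because the estimate moves towards 100%. At 89.0% with complete data, the binomial standard error is √(0.89 × 0.11 / 100) = 3.13 points, below the simulated 3.26. Loss widens the interval relative to complete data at the same estimate.

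It is also fair that visits by routine practice are deliberate in a non-interventional study, that the analysis is descriptive, and that part of SAP section 14.1 is redacted and Figure 1 is not shown. No claim is made here that a sensitivity analysis is missing. The point concerns what is collected, which analysis cannot repair.

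**Conclusion.** The gap is real: the primary endpoint depends on vital status through month 12, and the schedule plans no check of it. Informative censoring is a credible risk, not an established fact. A reader might conclude that the reported OS rate will be too high, but the documents give no loss rate and so do not support that.

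Upward bias is the likelier direction if departed patients go untraced. It can reverse if their deaths reach the site while survivors stay censored at their last examination under SAP section 9.6.

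Under the assumed inputs the overstatement is about 0.5 to 4 points: the lower part of the range if loss comes three months after progression, the upper part if it comes at progression. That is below the half-width of about 7 points. It would come near that half-width only if about half of progressors went untraced and true OS were near 80% or lower. The change is worth making because it is cheap and removes a systematic error that the interval does not show.

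**What to change.** 1. **Table 1:** add a survival-status row at month 12 and W104 for every patient not known to have died. Allow chart review, telephone, the treating physician or a registry, as local rules and consent permit.
2. **Protocol section 9.2.5:** attempt these checks before closing a patient as lost. Record separately whether a patient who stops visits or ePRO still permits survival follow-up.
3. **SAP section 9.6:** let the date last known alive from this check enter the last-contact derivation. As written, only dates of actual examinations count. Deaths found by telephone or registry would be events, while confirmed survivors stayed censored early, which would replace one bias with another.

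If status is obtained for everyone at month 12, the bias from untraced loss is zero and only sampling error remains.

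Cost: a small amendment, one eCRF field and at most 2 × 100 = 200 short checks. The change does not touch treatment or routine visits. The drawback is a slight extra workload for sites.
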